6.2 Functional Cognitive Endpoints

Prior to any formal statistical analyses of the cognitive and functional endpoints, each question, sub-domain and total score will be descriptively summarised and evaluated. Subsequently, formal statistical analysis of individual questions will only be performed and reported if any notable change from baseline is observed in the descriptive summaries. This process will be repeated at each analysis stage, i.e. Part 1 PD, Part 1 AD and Part 2 PD database locks.

For the Part 1 AD and Part 1 PD cohorts, the variables will be analysed using an ANOVA model of the Change from Baseline (Day 25 - Day 0). This will include Treatment group as a fixed effect, and LSmeans (with 95% CI) for this effect will be presented (Within group) together with Effect sizes ($(X_{Day\ 25} - X_{Base})/SD$). Between treatment group differences will also be presented for the comparison between Placebo and 80mg but interpreted cautiously.

For the Part 2 PD cohort with 4 treatment dose groups (5, 10, 20, 40mg) a similar ANOVA will be employed. However, the data from the Part 1 PD patients will also be included from both the Placebo and 80mg patient groups and combined with the Part 2 Parkinson patient data. Within and Between group ANOVA model analyses will then be employed in a similar manner to Part 1. However, in the Part 2 report, treatment group differences will include Placebo (from Part 1) versus each of the five active treatment groups, namely 5mg, 10mg, 20mg and 40mg from Part 2, and 80mg group from Part 1.

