5.2.1 Pharmacodynamic Endpoints

Pharmacodynamic endpoints are based on the assessments from protein levels in blood, plasma and CSF at the Baseline (0h Pre-dosing) and Day 25 (Confinement) visit (0h Pre-dosing, 1, 2, 3, 4, 5, 6h). Pre-dosing values at Baseline will be compared with Day 25 (Confinement) and derived as a percentage change from Baseline. The Percentage change from Day 25 0h pre-dose at 1, 2, 3, 4, 5 and 6h on Day 25 (Confinement) will also be derived and presented. The maximum percentage change determined over the 6h period may also be incorporated.

Table 3: Pharmacodynamic Endpoints

Pharmacodynamic measure	CSF	Plasma
Target Engagement		
aSYN monomers	X	
Aβ monomers:		
A β 40	X	X
A β 42	X	X
Soluble Amyloid Precursor Proteins:		
sAPP α	X	
sAPP β	X	
Tau Proteins:		
T-tau	X	X
P-tau	X	X
Pathway Engagement		
Axonal Transport:		
Neurofilament light (NfL)	X	X
Inflammatory factors:		
Complement 3	X	

	YKL40	X	
	sTREM2	X	
	GFAp	X	X
Synaptic factors:			
	SNAP25	X	
	Synaptotagmin	X	
	Neurogranin	X	
Control proteins:			
	Beta-trace protein	X	
Infective particles:			
	aSYN oligomers	X	
	A β oligomers	X	
Exosomes			X

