5.6 Other Definitions

Baseline, Study Day and Event Duration are specifically defined as:

Baseline

Two baselines are defined:

- 1 Last assessment prior to first dose of study IMP on Day 0.
- 2 At 0 hours on Day 25 of the Confinement visit

Study Day

Study Day = (Date of event - first dose of study IMP) + 1.

Event Duration

Event Duration= (Date of resolution – Date of onset) + 1

6. Statistical Methods.

This statistical analysis plan specifies the requirements for the analysis and reporting of all data collected during the study.

All analyses and data reporting procedures will be undertaken using SAS® v9.4 in a Windows version 10 operating system environment.

The descriptive statistics produced will account for the nature and distribution of the data collected. For continuous variables (actual and percentage change from baseline), data will be presented as number (n), mean, median, standard deviation, and range. For discrete variables (Incidence, Response outcome) data will be presented as frequencies and proportions and the denominator will be the number of patients available.

Data collected from patients in each of the three cohorts (Part 1 AD, Part 1 PD, Part 2 PD) will be derived and summarised as described in section 5 and analysed according to the defined analysis population in section 4.

All comparisons of primary interest performed in Part 1 and Part 2 involve changes from baseline (Within treatment group). The null hypothesis throughout is that there is no difference between the Day 25 end of treatment and Pre-treatment baseline (H0. $X_{end}=X_{base}$, H1. $X_{end} \neq X_{base}$).

Between treatment groups comparisons are also possible (but of secondary interest due to the small sample size). Here the null hypothesis is that there is no difference between any of the treatment groups at the end of treatment (H0. Placebo= $X_{5mg}=X_{10mg}=X_{20mg}=X_{40mg}=X_{80mg}$, H1. Placebo $\neq X_{5mg} \neq X_{10mg} \neq X_{20mg} \neq X_{40mg} \neq X_{80mg}$).

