6.1 Pharmacodynamic Endpoints

For the Part 1 AD and Part 1 PD cohorts, each variable measured in plasma and CSF will be analysed using an analysis of variance (ANOVA) model of the percentage changes from Baseline (between Baseline Day 0 Pre-dose 0h and Day 25 Pre-dose 0h). This will include Treatment group as a fixed effect and LSmeans (with 95% CI) for this effect will be presented (Within group).

Between group differences for 80mg vs Placebo will be assessed and presented (LSmeans +/- 95% CI) although results will be viewed cautiously given small control group samples size.

Then the percentage change from Baseline (Day 25 Pre-dose 0h) for each of the 6 hourly assessments will be analysed using a Repeated measured mixed model (RMMM) including Treatment group as a fixed effect, Time as the repeated effect and Subject as random term. Compound symmetry will be assumed for the covariance/correlation matrix. An overall average LSmean (with 95% CI) for the Treatment effect will be presented together with individual LSmean (with 95% CI) estimates for each hour. Treatment group differences will also be presented for the comparison between 80mg vs Placebo but the same caveat used given the control group subject sample size.

The maximum percentage change from Baseline (Day 25 Pre-dose 0h) over the 6 hours will also be analysed with an ANOVA model for both the Within treatment group and Between group (80mg vs Placebo) comparisons.

In the event of either model failing assumptions of normality or constant variance, a log transformed analysis of the actual values (*not percentage change*) will be substituted and the output estimates (means and 95% CIs) then back transformed by exponentiation to enable presentation of the ratio of values (%).

For the Part 2 PD cohort with 4 treatment dose groups (5, 10, 20, 40mg) the same analyses models will be employed. However, the data from the Part 1 PD patients will also be included (for those biomarker variables retained from Part 1 after evaluation at that stage) from both the Placebo and 80mg patient groups and combined with the Part 2 data. Within and Between group ANOVAs and RMMM model analyses will then be employed in a similar manner to Part 1. The Part 2 report of treatment group differences will include Placebo (from Part 1) versus each of the five active treatment groups, namely 5mg, 10mg, 20mg and 40mg from Part 2, and 80mg group from Part 1.

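### The Day 0 to Day 25 change-score ANOVAs leave out the Day 0 value as a covariate, so the secondary contrasts against 4 placebo patients carry part of any chance baseline imbalance

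*SAP*

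**What the plan says.** **Biomarkers (SAP 6.1).** Each plasma and CSF variable goes into an "analysis of variance (ANOVA) model of the percentage changes from Baseline (between Baseline Day 0 Pre-dose 0h and Day 25 Pre-dose 0h"), with treatment group as the fixed effect. If normality or constant variance fails, the substitute is "a log transformed analysis of the actual values", back-transformed to a ratio. No baseline term is stated for it.

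**Functional and cognitive scores (SAP 6.2).** Here "the variables will be analysed using an ANOVA model of the Change from Baseline (Day 25 - Day 0"), and "This will include Treatment group as a fixed effect". No other term is named.

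SAP 7.2 repeats these models without a baseline covariate, and Protocol 6.5 names none. The Day 0 values exist: SAP 5.2.1 takes biomarkers "at the Baseline (0h Pre-dosing) and Day 25 (Confinement) visit", and SAP 5.2.2 schedules the questionnaires at the same two visits.

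**Comparator.** SAP 3.3 randomises 10 active to 4 placebo in each Part 1 cohort. For the Part 2 report, SAP 6.1 and 6.2 compare the four Part 1 PD placebo patients with all five active PD groups.

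**Status.** SAP 2 and 6 make the within-group change the primary comparison and rank between-group comparisons second because of the sample size. SAP 6.1 and 6.2 ask for caution in reading them.

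**The concern.** Subtracting baseline, or dividing by it, is not the same as adjusting for it. Unless rho is 1, patients who start high tend to show a smaller rise or a larger fall. A group that starts high by chance therefore appears to change in a way that has nothing to do with the drug.

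The imbalance could be sizeable here. There are four controls. Neither Protocol 6.1 nor SAP 3.3 describes stratification on any baseline score. Entry ranges are wide (Protocol 8.1: MMSE 18–30 and Hoehn & Yahr up to 4 in PD, MMSE 18–28 in AD). In the 54-patient analysis the same four placebo patients serve all five contrasts, so an unusual placebo baseline moves all five in the same direction.

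These contrasts are the trial's only placebo-controlled evidence on biomarkers and function, and SAP 7.2 tabulates and plots them with confidence intervals.

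**Working it through.** **The plan's own figure.** SAP 3.1 Table 1 gives N = 9 per group for a 24% change in sAPPβ. The Protocol 6.2 table puts that at 1.4 SD. The two-group formula gives n = 2(1.960 + 0.842)²/1.4² = 8.01, rounded up to 9; the t-based value is 9.08. The figure reproduces as a comparison of two equal groups. It uses no covariate and no rho, so it says nothing for or against adjustment.

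**Inputs.**
- Group sizes: 10 v 4 in each Part 1 cohort (SAP 3.3); 4 placebo plus 5 × 10 active = 54 in the pooled PD analysis (SAP 6.1, 7).
- rho: not in the documents; assumed 0.5 to 0.9.
- Also assumed: equal SDs at both visits and bivariate normality.

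**Step 1: size of a chance imbalance.** SD of the baseline difference, 10 v 4: √(1/10 + 1/4) = 0.59 baseline SD.

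**Step 2: what reaches the contrast.** The change-score contrast carries −(1 − rho) times that difference. Its own standard error is √(2(1 − rho)) × 0.59.

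| rho | Shift from a 1-SD imbalance | SE of contrast | Shift/SE = √((1 − rho)/2) |
|---|---|---|---|
| 0.5 | 0.30 | 0.59 | 0.50 |
| 0.7 | 0.18 | 0.46 | 0.39 |
| 0.9 | 0.06 | 0.26 | 0.22 |

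The shift is already part of the standard error and does not add to it. Its effect shows when one looks at unlucky allocations. In simulated trials (20,000 per setting) where the active arm started more than 0.59 SD above placebo, the change-score contrast was off on average by −0.45, −0.26 and −0.09 baseline SD at rho 0.5, 0.7 and 0.9. The baseline-adjusted contrast (ANCOVA) was off by about 0. Over all randomisations, type I error was about 5% for both.

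**Step 3: interval width, ANCOVA relative to change score.** With N patients in g groups:

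ratio = √[ (1 + rho)/2 × (1 + 1/(N − g − 2)) ] × t(N − g − 1)/t(N − g)

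Example, N = 14, g = 2, rho = 0.5: √(0.75 × 1.1) × 2.201/2.179 = 0.918.

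| rho | N = 14, formula | N = 14, simulated | N = 54, formula |
|---|---|---|---|
| 0.5 | 0.918 | 0.91 | 0.876 |
| 0.7 | 0.977 | 0.97 | 0.932 |
| 0.8 | 1.005 | 1.00 | 0.959 |
| 0.9 | 1.033 | 1.03 | 0.986 |

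Break-even on width is rho ≈ 0.78 at N = 14 and ≈ 0.96 at N = 54. These figures are for absolute change. A separate check of percentage change with a log Day 0 covariate gave nearly the same ratios.

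**Step 4: scale against the real constraint.** With 10 v 4, 80% power needs a difference of 1.81 SD of change, against 1.32 SD with 10 v 10. For a 1.4 SD difference, power is about 58–59% with the change score. With ANCOVA it is 67%, 61%, 58% and 56% at rho 0.5, 0.7, 0.8 and 0.9.

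**Step 5: the cross-part contrasts.** Suppose, for illustration, that Part 2 patients differ from the Part 1 placebo group by d = 0.5 SD at baseline, with rho = 0.7 and no drug effect.
- If the group difference is stable, the change score expects 0 and ANCOVA is off by (1 − 0.7) × 0.5 = 0.15 SD.
- If both groups regress to a common mean, ANCOVA expects 0 and the change score is off by −0.15 SD.

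The documents do not say which holds.

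**The case against.** The strongest reply is that this touches only comparisons the SAP already ranks second and marks for caution. The trial's primary outcomes are safety and PK. SAP 2.1.2 expects no clinical benefit and wants the functional scores mainly for variability estimates. The limit on precision is four controls, which a covariate cannot cure. This stands as a limit on importance: the primary within-group estimates are unaffected. It does not justify ignoring a measured baseline, because the contrasts will still be reported with intervals.

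Four stronger readings are tempting, and the documents do not support them:

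- *Every between-group model is a change score with treatment alone.* The hourly mixed model is specified as "including Treatment group as a fixed effect, Time as the repeated effect and Subject as random term". The fallback uses log actual values. The hourly and maximum-change analyses take their baseline "At 0 hours on Day 25 of the Confinement visit", an on-treatment value. The point does not extend to those two analyses.
- *The unadjusted 80 mg contrast is biased.* Under randomisation both methods are unbiased on average and hold their type I error. Counting imbalance and noise as two separate harms would count one thing twice.
- *Adjustment always sharpens the estimate.* In the 14-patient cohorts it does so only below rho of about 0.8.
- *Adjustment repairs the Part 2 comparison with Part 1 placebo.* It does not. Those groups were not randomised against each other, and Step 5 shows that either method can be the wrong one.

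**Conclusion.** The concern holds for the Day 0 to Day 25 pre-dose ANOVAs in SAP 6.1 and 6.2. They omit a baseline value the trial collects, and the secondary contrasts against four placebo patients carry (1 − rho) times any chance baseline imbalance.

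The size is modest and depends on an undocumented rho. Over 0.5 to 0.9, adjustment changes the 95% CI from about 9% narrower to 3% wider at N = 14, and makes it about 12% to 1% narrower in the 54-patient PD model. The clearer gain in Part 1 is protection when the allocation happens to be unbalanced. The estimates rest on equal SDs at the two visits, approximate normality and a common slope. The small placebo group remains the larger limit on these contrasts.

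**What to change.** - **Between-group contrasts, Day 0 to Day 25 models (SAP 6.1 and 6.2):** add the Day 0 value as a covariate. Use the log Day 0 value when a biomarker is analysed on the log scale, including the log actual-value fallback.
- **Within-group estimates:** keep them as paired changes, as now.
- **Pooled PD analysis, 5–40 mg versus Part 1 placebo:** show the unadjusted change contrast beside the adjusted one. State that the groups were not randomised against each other, that neither method removes that bias, and which assumption each relies on.

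**Cost.** One term and one error degree of freedom per model; a common slope across groups, one of which has four patients; and intervals up to about 3% wider in the 14-patient cohorts if rho is near 0.9. Between-group estimates will no longer equal the difference of the within-group means. The shared model tables in SAP 7.2 (for example 14.2.1.2 and 14.2.1.3) will therefore need to show two models, with a footnote saying so.

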6.3 Safety Endpoints

All safety data will be summarised according to cohort and treatment dose group. Presentation formats of the data described in section 5 are given in section 7. For consistency with the pharmacodynamic and functional cognitive data analyses, the data from the Part 1 Parkinson patients will also be included from both the Placebo and 80mg patients and combined with the Part 2 Parkinson patient data for the third analysis.

6.4 Pharmacokinetic Endpoints

All PK analyses will be done on completion of Part 2, including the data from the Part 1 AD and PD patients.

6.4.1 Part 1 AD, Part 1 PD Cohort

All derived parameters for these patient groups will be presented descriptively as outlined in section 5.4. No formal analyses will be performed with the AD patient data. However, the 80mg PD patient data will be combined and included with the analysis of the four Part 2 Posiphen treatment groups.

For actual drug concentrations descriptive statistics (arithmetic mean, minimum, median, maximum, coefficient of variation (CV), standard deviation (SD) and number of observations) will be used and displayed graphically as arithmetic mean (\pm SD) plasma drug concentration value versus time (nominal) for each treatment/dose group using a log-linear format.

The derived pharmacokinetic parameters will also be displayed using descriptive summaries (arithmetic mean, standard deviation, coefficient of variation, geometric mean, median, minimum, maximum and number of observations) for each cohort and treatment/dose group. If appropriate, geometric means will be displayed in addition to the arithmetic mean.

[figure not shown]
6.4.2 Part 2 PD Cohort

Although the PK parameters will be presented as for Part 1 (according to Treatment dose group) the C_{max} and AUCs will also be formally analysed to evaluate the relationship between the ascending dose groups (Dose-proportionality as in Figure 1). In addition to the patients from the four treatment groups in Part 2 (5mg, 10mg, 20mg and 40mg), the 80mg group of PD patients from Part 1 will be included.

This will involve an ANOVA power model using the log transformed individual patient derived parameters as an explanatory variable and with Treatment dose group as the dependent fixed effect. In the event of demonstrating an overall statistically significant difference, comparisons between all pairs of means will be performed using the Scheffe method. LSmeans point estimates with 95% CIs derived will be presented after back transformation (exponentiation) of all pairwise differences between doses as ratios (%). Significant differences ($p < 0.05$) in the ratio of any two doses will be declared if the 95% confidence interval excludes 100%.

The regression slope (Figure 1) of the log transformed PK parameter against log Dose represents the power model ($\log(AUC) = a + b * (\text{Dose})$) where 'a' represents the intercept and 'b' the coefficient for linear slope). Therefore, a 90% confidence interval for the estimate of the slope excluding $b=1$ will indicate significant departure from linearity.

Figure 1: Dose Proportionality (Log PK Parameter vs Log Dose)

For the dose difference analysis, all dose group estimates will be presented as LS means with 95% CIs after back transformation of the log values and all pairwise comparisons with the lowest dose will be presented as ratios of LS means (%) with 95% confidence intervals. These will be presented graphically.

For both the Differences between doses and Dose proportionality analyses of the C_{max} and AUC parameters summaries of the model applied with Mean square error, Degrees of freedom, F statistic and resulting p-value for each model parameter will be displayed.

For Dose proportionality the coefficient of the linear slope (b) will be presented as a point estimate with 90% CI together with plots of $\log C_{max}$ vs Dose and $\log AUC$ vs Dose.

7. Presentation.

As each cohort completes (Part 1 AD, Part 1 PD, and Part 2 PD) these data will be unblinded and the pharmacodynamics (Biomarkers in CSF and plasma), efficacy, and safety will be evaluated and presented accordingly.

Once all patients in Part 2 have completed, the PK data and infective particle and exosomes data from all three cohorts will be made available and analysed separately.

Summaries will be presented by cohort and treatment, visit and time recorded as appropriate.

The table below summarises the schedule for presentation of each cohort's statistical report output:

Analysis	Cohort	Deliverables
1	Part 1 – PD Patients (14)	Disposition Tables and Listings Biomarker* Tables, Figures and Listings Functional/cognitive Tables, Figures and Listings Safety Tables and Listings
2	Part 1 – AD Patients (14)	Disposition Tables and Listings Biomarker* Tables, Figures and Listings Functional/cognitive Tables, Figures and Listings Safety Tables and Listings
On completion of Part 2:		
3	PD Patients (54) – including 14 PD patients from Part 1 and 40 PD patients from Part 2	Disposition Tables and Listings Biomarker* Tables, Figures and Listings Functional/cognitive Tables, Figures and Listings Safety Tables and Listings
4	PD Patients (50) – including ten 80mg PD patients from Part 1 and forty PD patients (5mg, 10mg, 20mg and 40mg) from Part 2 AD Patients (10) – 80mg patients from Part 1 All patients (68) from Part1 and Part 2	PK analyses Tables, Figures and Listings PK analyses Tables, Figures and Listings Infective Particles in CSF: Tables, Figures and Listings Exosomes in plasma: Tables, Figures and Listings

*Biomarker results (excluding infective particles and exosomes) from assays conducted in Part 1 will be evaluated by the Sponsor and will inform the choice of assays and subsequent output from Part 2

NB: Infective particles and exosomes biomarker data will not be presented until after the completion of Part 2

Detailed ‘table shells’ for Part 1 and Part 2 will be produced to accompany this SAP. These not only describe table layout but table numbering formats and also the level of accuracy (number of decimal places) to be described in each table.

The following described tables and figures will be included in the statistical report.

7.1 Study Status.

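### SAP 6.4.2 contradicts itself on the dose-proportionality model: one sentence reverses response and explanatory variable, and the formula beside the b=1 rule leaves Dose unlogged

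*SAP*

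**What the plan says.** SAP section 6.4.2 (Part 2 PD Cohort) plans two formal analyses of Cmax and AUC: a comparison between dose groups, and a dose-proportionality regression. It covers the four Part 2 doses, and "the 80mg group of PD patients from Part 1 will be included".

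- **Dose-group analysis.** The model is described as "using the log transformed individual patient derived parameters as an explanatory variable and with Treatment dose group as the dependent fixed effect". The same paragraph then asks for LS means and for back-transformed pairwise ratios between doses.
- **Power model in words.** "The regression slope (Figure 1) of the log transformed PK parameter against log Dose represents the power model".
- **Power model as a formula.** The bracket in that same sentence reads log(AUC) = a + b*(Dose), with a as intercept and b as slope.
- **Decision rule.** A 90% confidence interval for the slope that excludes b=1 "will indicate significant departure from linearity".
- **Figure.** Its title is "Figure 1: Dose Proportionality (Log PK Parameter vs Log Dose)".
- **Planned output.** The slope b is to be reported with a 90% interval, and the accompanying graphs show log Cmax and log AUC, each against Dose, with no log on Dose.

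SAP section 7.4 lists the dose-proportionality output again but does not restate the model, so it does not resolve the difference.

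**The concern.** There are two separate defects in one section.

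First, the sentence on the dose-group ANOVA names the PK parameter as explanatory and the dose group as dependent. The outputs requested there exist only if the log PK parameter is the response and dose group is a factor.

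Second, the proportionality model is given in two forms that are not equivalent. The words and the figure title are log-log; the formula and the plot description have log PK against unlogged Dose. The value b=1 means proportionality only when both variables are logged. With unlogged Dose, b is a rate per mg and 1 has no special meaning.

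Plasma PK is a primary outcome (Protocol synopsis), support for potential dose-proportionality analyses is one stated reason for 10 patients per dose (Protocol 6.2, SAP 3.1), and SAP 6.4.2 holds the SAP's only formal PK inference. A false finding of departure might also pass unnoticed, because Protocol 3.2 reports that Cmax rose disproportionately with dose in the earlier multiple-dose study.

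**Working it through.** **Inputs.** Doses 5, 10, 20, 40 and 80 mg (SAP 6.4.2); 10 PD patients per dose, n = 50 (schedule table in SAP section 7); 90% interval with 48 degrees of freedom, t = 1.677. The documents give no between-patient CV for this analysis, so 30%, 60%, 100% and 200% are assumed, log-normal, with SD on the ln scale = sqrt(ln(1 + CV²)).

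**Step 1: reproduce the plan's reference value.** Under proportionality AUC = c × Dose, so ln(AUC) = ln(c) + 1 × ln(Dose). The log-log slope is exactly 1, as the rule assumes.

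**Step 2: the slope from the formula as it reads.** Mean dose = 155/5 = 31.
- Dose deviations: −26, −21, −11, 9, 49. Sum of squares = 676 + 441 + 121 + 81 + 2401 = 3720.
- ln(Dose) deviations, in units of ln 2: −2, −1, 0, 1, 2. Sum of cross-products = 52 + 21 + 0 + 9 + 98 = 180.
- Slope = 0.6931 × 180 / 3720 = 0.0335 per mg (0.0146 with log10).

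**Step 3: how far this is from 1.** If the true exponent is p, the expected slope is 0.0335 × p, so a slope of 1 needs p = 1/0.0335, about 30. For the interval to reach 1 under proportionality, with 10 patients per dose (sum of squares 37,200), the residual SD on the ln scale would have to be (1 − 0.0335)/1.677 × sqrt(37,200), about 111. At CV 200% the SD is sqrt(ln 5) = 1.27.

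**Step 4: simulation under exact proportionality**, 5,000 trials per setting. Entries are the share of trials in which the 90% interval excludes 1.

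| Assumed CV | log PK on log Dose | log PK on unlogged Dose | log Dose on log PK (mean slope) |
|---|---|---|---|
| 30% | 9.7% | 100% | 64% (0.92) |
| 60% | 10.9% | 100% | 98% (0.77) |
| 100% | 10.5% | 100% | 100% (0.59) |
| 200% | 9.8% | 100% | 100% (0.38) |

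For unlogged Dose the largest upper limit in any of these trials was 0.067. The share was also 100% with true exponents of 0.7, 1.5 and 2.0.

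**Step 5: which text causes what.** The second column of results comes from the unlogged Dose in the formula. The last column shows what would happen if the role reversal were carried over into the b=1 regression; the SAP does not say this, since the reversed sentence concerns the dose-group ANOVA. In that ANOVA the reversal cannot be followed together with the outputs requested, because LS means by dose and ratios between doses need log PK as the response.

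**The case against.** The strongest reply is that the intended model is plain. The sentence that holds the formula says log Dose, the b=1 rule follows directly from that sentence, Figure 1 is titled log-log, and the term power model itself implies logs on both sides. On that reading the rule works at its nominal level. An experienced PK programmer would probably fit it, and a slope near 0.03 set against 1 would draw attention at quality control. This stands. A reader might infer from the formula that the planned rule would always declare departure; the documents do not support that, because the formula is only one of two conflicting statements and the words around it are right.

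The missing log may also not be in the SAP. The text reviewed was extracted from a PDF, and the bracket around the formula has one closing parenthesis too many; restoring a lost opening log before Dose would balance it. The original page will settle this. The plot description, a second place without a log on Dose, points the other way, although a plot label alone does not alter the slope or the test.

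Finally, Protocol 6.4 makes dose proportionality optional, as appropriate. That bears on severity. None of this explains the role reversal, which is ordinary prose and which no extraction fault would produce.

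**Conclusion.** The section needs correction. The role reversal is an error as written. The proportionality model has two incompatible statements, and only the log-log one fits the b=1 rule. The consequence is conditional: coded from the formula, the slope under proportionality is about 0.034 per mg and the interval excludes 1 essentially whatever the data show; coded from the words and Figure 1, false departure is 9.7% to 10.9% against a nominal 10%.

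The 0.034 rests only on the planned doses and equal group sizes. The simulated rates rest on assumed CVs of 30% to 200%, and the contrast between the two models is the same across that range. The role reversal should not be blamed for the 100% figure.

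This is a low-cost correction of the specification and not a must-fix item, because no dose decision, stopping rule or gate in the documents depends on the test.

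**What to change.** In SAP 6.4.2:

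1. State the proportionality model as ln(PK parameter) = a + b*ln(Dose), with ln(PK parameter) as the response and ln(Dose) as a continuous explanatory variable, for Cmax and each AUC.
2. Say that the 90% interval and the b=1 rule apply to this slope only.
3. Make the planned Cmax and AUC plots log-log, to match Figure 1.
4. In the separate dose-difference ANOVA, name log PK parameter as the response and dose group as the fixed factor.
5. Check the formula on the original page; if it already shows log of Dose, item 1 only confirms it.

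The cost is SAP wording and matching plot templates. No new data, patients or design change are needed. All PK analyses are scheduled for after Part 2 is complete, so the text can be corrected before any is run.
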